PROTOCOL

TITLE:

Abdominal drainage in the postoperative period of liver transplantation (DRALIT):
multi-institutional randomized clinical trial

Drenaje abdominal en el postoperatorio del trasplante hepático (DRALIT): Ensayo Clínico
multicéntrico aleatorizado.

Protocol code:

Version: v.1

Date: 24/5/2022

EudraCT:

PROMOTER: Department of General Surgery and Digestive Diseases

PRINCIPAL RESEARCHER / COORDINATOR: [name] / [name]

CONFIDENTIAL

This document contains confidential information that should not be disclosed or published to other people other than clinical researchers, members of the Clinical Research Ethics Committees of the participating hospital centers and Spanish Health Authorities.

ABSTRACT

Title:

Abdominal DRAINage in the postoperative period of Liver Transplantation (DRALIT): multi-institutional randomized clinical trial

Promoter: Department of General Surgery and Digestive Diseases

Principal researchers:

[name]. FEA General and Digestive System Surgery Service. Virgen de la Arrixaca University Clinical Hospital.

[name]. General Surgery and Digestive System Resident. Virgen de la Arrixaca University Clinical Hospital.

Justification of the study: Classically, in the postoperative period of liver transplantation (LT), abdominal drainage has been used as a way to make the early diagnosis of hemorrhages, bile leaks and other postsurgical complications, as well as an evacuation route for ascites. The use of it routinely is currently under discussion due to the morbidities associated with its use.

Objectives: The objective of the clinical trial is to evaluate whether the routine use of abdominal drainage in the postoperative period of LT is associated or not with an increase in postoperative complications. Also evaluate the quality of life in relation to the presence or not of abdominal drainage.

Trial design: After signing the informed consent of those patients who meet the inclusion criteria, they will be randomized into two groups for placement of an abdominal drain or not. On the third day, the abdominal drainage will be removed except for signs of bleeding, postoperative infection or bile leakage, and abdominal postoperative complications will be evaluated according to the Clavien-Dindo scale in the first 90 postoperative days.

Randomization: 2 groups of equal size, total n = 365 patients. Simple intraoperative randomization prior to closure of the abdominal wall after fulfilling all the inclusion criteria and none of the exclusion criteria.

Masking: no masking.

Study population: liver transplants for all etiologies.

Variables analyzed:

- **Recipient preoperative** variables: gender, age, pre-transplant stay, BMI, ASA, diabetes, HTN, dialysis, MELD, Child-Pugh, serology, albumin, bilirubin, INR, CRP, creatinine, ascites, SBP, prothrombin time, encephalopathy, time from SSI to LT (months), retransplantation, previous surgeries, cirrhosis etiology, indication for transplantation, sarcopenia.
- **Donor** characteristic variables: age, stay in ICU, vasoactive drugs, cultures, antibiotics, CIT, WIT, type of donation (DBD / DCD), previous immunosuppression.
- **Intraoperative** variables: placement or not of abdominal drainage, surgical time (min), transfusions, blood loss, surgical technique, arterial anastomosis type, biliary anastomosis type, donation with extended criteria, recipient with extended criteria, clamping times.
- **Postoperative** variables: ICU stay, hospital stay, abdominal complications (collection, bile leak, hematoma, hemorrhage, paralytic ileus, ascites, bleeding, wound drainage complications, vascular anastomosis complications, mechanical obstruction, hollow viscus perforations, wound complications surgery), graft function, post-transplant antibiotic therapy, post-transplant immunosuppressive regimen, number of post-LT HC, mortality at 90 days, global complications at 90 days.
- **SF-36:** Physical function, physical role, body pain, general health, vitality, social function, emotional role, mental health (on inclusion in the waiting list, one month after surgery, 4 months after surgery).

● INDEX	Page
○ Summary	3
○ Index	5
○ List of acronyms and definition of terms	6
○ General Information	7
○ Justification	10
○ Objective and purpose of the study	11
○ Study design	11
○ Study population	14
○ Treatment of subjects	15
○ Study variables	17
○ Follow-up of subjects	17
○ Safety assessment	17
○ Statistics	18
○ Ethics	20
○ Informed Consent	21
○ Direct access to source data / documents	21
○ Data management and record file.....	21
○ Data protection	22
○ Financing and insurance	22
○ Publication policy	22
○ Bibliography	23
○ Annexes	25

LIST OF ACRONYMS AND DEFINITION OF TERMS

- **ASA:** American Society of Anesthesiologists Classification
- **BMI:** Body Mass Index

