In transplant patients, the use of post-surgical abdominal drains on a routine basis has shown an increase in total protein losses in patients with refractory ascites, an increase in ascending infections secondary to drainage, infection and pain at the insertion point of the drain, as well as as, an increase in hospital stay. Nor can a higher rate of postsurgical bleeding and bile leakage be ruled out in patients with abdominal drainage.

Currently, in the few studies that there are in reference to the systematic use of abdominal drains in ITH, the need for them prophylactically is being discussed as an early diagnosis of postoperative intra-abdominal complications is not observed, but complications are seen to increase secondary to drainage. Therefore, the need to use it systematically in all patients is currently under discussion.

Currently, we are facing an increase in ERAS® (Enhanced Recovery After Surgery) programs, which began in 2008 with colorectal surgery and are currently expanding to other surgical procedures. These programs advocate reducing the number of drains and even not using them in patients with a low risk of post-surgical complications.

In the current bibliography, the methodology of the studies is varied, with the majority being non-randomized retrospective studies, which is why it is a subject that requires studies with a better methodological design and a higher number of patients to obtain

conclusions of clinical relevance. that can set the direction in this area that is in constant discussion.

Given the absence of any randomized non-inferiority clinical trial that studies the routine use of abdominal drainage in the postoperative period of liver transplantation, we consider that it is necessary to carry it out to increase the evidence.

The number of HT performed in each center is limited and variable annually, which is why we consider that the best design for this clinical trial is a European multicenter.

- **OBJECTIVE AND PURPOSE OF THE TEST**

The objective of our randomized clinical trial is to evaluate whether the prophylactic use of intra-abdominal drains in LT patients reduces postoperative intra-abdominal complications, compared to their routine use.

- **Main goal.**
 - To assess whether the prophylactic use of abdominal drains in the postoperative period of LT increases the number of abdominal complications in the 90 postoperative days (Clavien-Dindo)
- **Secondary objectives.**

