 - To evaluate the possible improvement in the quality of life of the transplanted patient derived from the absence of postsurgical drainage (SF-36).
 - Evaluate the postoperative stay in both groups.

- **STUDY DESIGN**

Unmasked European multicenter randomized clinical trial with two arms parallel to the study.

Patients who meet the inclusion criteria will be offered to participate in this study by signing an informed consent. An informed consent approved by the Research Ethics Committee of the Virgen de la Arrixaca University Hospital will be used.

Patients who give their consent for the study will be randomized to the drainage group (D) and the control group without drainage (ND) before the beginning of the abdominal wall closure.

In the drainage group (D), it will be placed on the right flank / right iliac fossa. The drain will be connected to a bag and fixed to the skin with a silk. Said drain will be placed at the level of the surgical bed.

Regarding the control group, intraoperative drainage will not be placed, except when the surgeon's discretion considers it necessary due to the high risk of bleeding, bile leakage or any other process / complication in which it may benefit from intra-abdominal drainage.

All patients, regardless of the randomization group, will receive a quality of life questionnaire (SF-36) prior to surgery that they must complete.

All patients will receive routine antibiotic prophylaxis 60 minutes before surgery, repeating the number of doses that are required according to blood loss and surgical time. Antibiotic prophylaxis will be adjusted according to the resistance protocols of each participating center.

○ **DATA COLLECT**

The following variables will be collected for each patient:

- **Recipient preoperative** variables: gender, age, pre-transplant stay, BMI, ASA, diabetes, HTN, dialysis, MELD, Child-Pugh, serology, albumin, bilirubin, INR, CRP, creatinine, ascites, SBP, prothrombin time, encephalopathy, time from SSI to HT (months), retransplantation, previous surgeries, cirrhosis etiology, indication for transplantation, sarcopenia.
- **Donor** characteristic variables: age, stay in ICU, vasoactive drugs, cultures, antibiotics, CIT, WIT, type of donation (DBD / DCD), previous immunosuppression.

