Once the individual has signed the informed consent document for the study and it has been verified that they meet all the inclusion criteria and none of the exclusion criteria, they will be considered eligible to be included in the study. In this first contact with the patient, you will fill out a first SF-36 health questionnaire.

Each patient will be assigned a numerical code consecutively as they are included in the trial. Randomization should be done in the operating room at the time prior to abdominal wall closure (optimal time for drain placement). This moment is chosen for randomization to avoid randomizing patients who ultimately require drainage due to intraoperative conditions by decision of the surgeon and not by randomization. Randomization will be performed using a spreadsheet with restricted access to participating centers through simple randomization. In order to carry out the randomization, the sheet will require filling in the initial data of the patient with which it will be verified that he meets the inclusion criteria in the study and none of the exclusion criteria. Subsequently, he will proceed to randomization and assign a number to the patient.

- **STUDY POPULATION**

- **Definition of the study population**

Patients will be recruited into the transplantation committee of the Hospital Clínico Virgen de la Arrixaca University. 365 individuals will be selected from both sexes, aged between 18 and 75 years, diagnosed with cirrhosis, liver disease, fulminant hepatitis or other indications specific to HT.

- **Inclusion criteria.**

- Patients of both sexes aged between 18 and 75 years included in the waiting list for HT by the committee of the Virgen de la Arrixaca University Hospital.
- Sign Informed Consent.

- **Exclusion criteria.**

- Having been rejected for liver transplantation by said committee.
- Age less than 18 years or greater than 75.
- Any contraindication by the main surgeon that makes the placement of an intra-abdominal drain necessary.
- Not having signed the Informed Consent.

- **Abandonment and replacement of patients.**

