The Principal Investigator will ensure that subject identification codes are kept for at least fifteen years after the trial has been completed or discontinued.

The data of all the CRDs will be entered into a database created for this purpose and equipped with safety margins and internal coherence standards. This database will be equipped with a double entry system and filters that prevent and detect any type of inconsistency or error in it. The information will be validated through internal consistency controls, studying the missing values. The data will be verified and corrected until the

database is fully validated. Once the database is purged, the variables will be recoded generating new variables (regrouping, sums, etc.).

- **Sample size.**

The hypothesis of this study was that the risk of postoperative complications at 90 days in the ND group would not be higher than in group D. A non-inferiority configuration was selected because the omission of drain placement is advantageous in terms of relieving to patients from discomfort and a decrease in medical cost. In calculating the sample size, the risk of an early postoperative complication related to LT was assumed to be 9% in the drain group and 6% in the no-drain group according to the literature review performed. Under a 4% non-inferiority margin, an alpha error of 0.05, and a statistical power of 80%, the sample was calculated as 174 patients in each arm. Assuming a 5% dropout rate, a total of 365 patients will be recruited into this study.

- **Statistic analysis**

The subsequent statistical analysis will be performed with the SPSS v.25 software.

- **Descriptive analysis.**

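### The plan promises equal arms but uses simple randomisation, and it controls for centre in neither the allocation nor the primary analysis; the cost is small and the remedy cheap

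*Combined protocol and SAP*

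**What the plan says.** The Randomization entry of the abstract gives "2 groups of equal size, total n = 365 patients" and, in the next sentence, "Simple intraoperative randomization prior to closure of the abdominal wall". The section on sampling and assignment repeats the method: "Randomization will be performed using a spreadsheet with restricted access to participating centers through simple randomization". The text supplied mentions no blocks, strata, minimisation or other balancing device.

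Study design calls this an "Unmasked European multicenter randomized clinical trial with two arms parallel to the study". The text just before the objectives explains why several centres are needed: "The number of HT performed in each center is limited and variable annually". At least one element of care is set locally: "Antibiotic prophylaxis will be adjusted according to the resistance protocols of each participating center". Study population, however, says "Patients will be recruited into the transplantation committee of the Hospital Clínico Virgen de la Arrixaca University", and the inclusion criterion names the same single committee.

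Under Statistics, the analysis of the main variable is a comparison of complication incidence, with no centre term. A general univariate and multivariate exploration of the collected variables is also planned, but centre is not in the variable lists.

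**The concern.** Simple randomisation gives each patient an independent 50:50 chance. Equality then holds only on average, so the abstract claims a property that the design does not have.

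The second part concerns centre. If centres differ in their complication risk, a small centre that happens to place most of its patients in one arm moves the estimated risk difference for reasons unrelated to drainage. The primary comparison is judged against a 4-point non-inferiority margin, so this is variation worth removing if removal is cheap. As written, neither the allocation nor the primary analysis does so.

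**Working it through.** **Inputs.** From the Sample size section: complication risks "assumed to be 9% in the drain group and 6% in the no-drain group", margin 4 points, alpha 0.05 (sidedness not stated), power 80%, 174 per arm, 5% dropout, total 365. Number of centres, centre sizes and between-centre variance: not given, so assumed below.

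**1. The plan's own figure.** The distance from the expected difference to the margin is 0.04 − (0.06 − 0.09) = 0.07. With unpooled variance,

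n per arm = (0.09×0.91 + 0.06×0.94) × (1.645 + 0.842)² / 0.07² = 0.1383 × 6.183 / 0.0049 = 174.5.

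This agrees with 174, but only for one-sided alpha 0.05; one-sided 0.025 gives 222. For dropout, 348 × 1.05 = 365.4, which is the stated 365.

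**2. Arm sizes under simple randomisation.** One arm follows Binomial(365, 0.5), with SD √365/2 = 9.55.
- 95% range: 182.5 ± 1.96 × 9.55, or 164 to 201 (exact quantiles agree).
- P(both arms at least 174) = P(174 ≤ X ≤ 191) = 0.654, so P(one arm below 174) = 0.346.
- P(183/182, the best possible split) = 0.08.

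**3. What that costs in power.** Power = Φ(0.07/SE − 1.645), with SE² = 0.0819/n(drain) + 0.0564/n(no drain), before dropout.

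| Drain / no drain | Power |
|---|---|
| 183 / 182 | 81.6% |
| 164 / 201 | 80.6% |
| 201 / 164 | 81.8% |

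Averaged over all splits, power is 81.4%. The loss is about 1 point at worst.

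**4. Splits within a centre (assumed sizes).** For a centre of 20, P(13:7 or worse) = 0.26. For a centre of 10, P(7:3 or worse) = 0.34.

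**5. Effect of centre imbalance on the risk difference.** Assumptions: 10 equal centres, 365 patients, overall risk held at 7.5% (the mean of 9% and 6%), between-centre SD of 0.5 to 1.0 on the log-odds scale. Simulated shift in the risk difference from centre mix alone:
- SD about 0.36 points (log-odds SD 0.5) to 0.72 points (log-odds SD 1.0);
- probability of a shift above 1 point about 1% to 13%. Runs that hold the 7.5% in slightly different ways put the upper end between 13% and 14%.

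**6. Is this extra to the planned error?** No. In simulation under the same centre assumptions, the true SD of the estimated difference was 2.77 to 2.78 points, against a mean reported standard error of 2.74 to 2.75. The ordinary binomial variance at the overall risk already includes the between-centre part.

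**7. What removing it gains.** At equal arms (182.5 each) the SE is 2.753 points and power is 81.5%. Removing a component of 0.36 points gives √(2.753² − 0.36²) = 2.729 and power Φ(7/2.729 − 1.645) = 82.1%. Removing 0.72 points gives 2.657 and 83.9%.

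**The case against.** The best defence is that simple randomisation is a valid choice. It is unbiased, its standard error is honest about chance imbalance, and in an unmasked trial it cannot be guessed. Here that last property matters, because the surgeon may exclude a patient as needing a drain immediately before allocation, which is when a predictable block would be most damaging. The equal-size phrase can be read as loose wording for a 1:1 ratio. All of this stands, and it limits the point to balance and modest efficiency.

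It does not remove the point. The wording still states something the method does not provide, and a defence of simple allocation would normally be paired with a centre-adjusted analysis, which is absent.

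Four stronger readings may tempt a reader, and the documents do not support them:
- *The trial is underpowered because an arm may fall below 174.* Step 3 shows power stays at 80.6% or more across the 95% range of splits before dropout.
- *Centre imbalance adds error on top of the planned error, or biases the result.* Step 6 shows it is already inside the planned standard error. Shift SDs as high as 0.93 points, with a 22% chance of exceeding 1 point, arise only if overall risk is allowed to drift above the planned 7.5%.
- *Differences in centre follow-up distort the endpoint.* Each centre's own follow-up starts after the day-90 call, whereas the main objective counts complications within 90 postoperative days.
- *Surgeons' differing thresholds for a drain unbalance the arms.* The documents do not say that thresholds differ, and the randomisation and safety sections place that decision before allocation. The Study design text allowing a drain in controls conflicts with this, but stratification would not resolve that conflict.

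**Conclusion.** The point holds in a limited form. The promise of equal arms contradicts the stated method, whatever the number of centres, and centre is handled in neither the allocation nor the primary analysis. There is no bias, and unequal totals cost at most about 1 point of power. On the assumptions in step 5, the avoidable component has an SD of about 0.4 to 0.7 points against a 4-point margin, and removing it would raise power from 81.5% to roughly 82% to 84%.

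The arm-size figures are exact. The centre figures rest wholly on an assumed number of centres and assumed between-centre variation. That centre predicts complications is plausible, given locally set prophylaxis, but the documents do not show it. If recruitment really ran through one hospital's committee, the centre part would fall away and only the wording point would remain. The change is worth making because it is cheap, not because the trial fails without it.

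**What to change.** 1. In the abstract and the randomisation section, replace simple randomisation with 1:1 permuted blocks stratified by centre, with block sizes that vary at random and are concealed from the sites.
2. Make the total even, or replace the equal-size statement with a 1:1 allocation ratio. For reference, 174/0.95 = 183.2, so 184 per arm, or 368 in all, also allows for 5% dropout by division.
3. Add centre to the collected variables.
4. Prespecify the primary risk difference and its confidence interval as stratified by centre, for example Mantel-Haenszel. Blocking alone would leave the unadjusted standard error slightly too large, so the analysis should follow the design.
5. Reconcile the single-committee recruitment and inclusion text with the multicentre design.

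**Cost.** Protocol wording, a new allocation list in the existing spreadsheet and one extra data field. Stratification needs no extra patients; an even total adds one patient, or three if 368 is used. The downside is slight predictability within a centre in an unmasked trial where a patient can be excluded just before allocation. Hidden, varying block sizes limit this. If it is still judged unacceptable, keep simple randomisation, correct the equal-size wording and prespecify the centre-adjusted analysis, which should recover much of the efficiency without touching the allocation.

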In transplant patients, the use of post-surgical abdominal drains on a routine basis has shown an increase in total protein losses in patients with refractory ascites, an increase in ascending infections secondary to drainage, infection and pain at the insertion point of the drain, as well as as, an increase in hospital stay. Nor can a higher rate of postsurgical bleeding and bile leakage be ruled out in patients with abdominal drainage.

Currently, in the few studies that there are in reference to the systematic use of abdominal drains in ITH, the need for them prophylactically is being discussed as an early diagnosis of postoperative intra-abdominal complications is not observed, but complications are seen to increase secondary to drainage. Therefore, the need to use it systematically in all patients is currently under discussion.

Currently, we are facing an increase in ERAS® (Enhanced Recovery After Surgery) programs, which began in 2008 with colorectal surgery and are currently expanding to other surgical procedures. These programs advocate reducing the number of drains and even not using them in patients with a low risk of post-surgical complications.

In the current bibliography, the methodology of the studies is varied, with the majority being non-randomized retrospective studies, which is why it is a subject that requires studies with a better methodological design and a higher number of patients to obtain

conclusions of clinical relevance. that can set the direction in this area that is in constant discussion.

Given the absence of any randomized non-inferiority clinical trial that studies the routine use of abdominal drainage in the postoperative period of liver transplantation, we consider that it is necessary to carry it out to increase the evidence.

The number of HT performed in each center is limited and variable annually, which is why we consider that the best design for this clinical trial is a European multicenter.

- **OBJECTIVE AND PURPOSE OF THE TEST**

The objective of our randomized clinical trial is to evaluate whether the prophylactic use of intra-abdominal drains in LT patients reduces postoperative intra-abdominal complications, compared to their routine use.

- **Main goal.**
 - To assess whether the prophylactic use of abdominal drains in the postoperative period of LT increases the number of abdominal complications in the 90 postoperative days (Clavien-Dindo)
- **Secondary objectives.**
 - To evaluate the possible improvement in the quality of life of the transplanted patient derived from the absence of postsurgical drainage (SF-36).
 - Evaluate the postoperative stay in both groups.

- **STUDY DESIGN**

Unmasked European multicenter randomized clinical trial with two arms parallel to the study.

Patients who meet the inclusion criteria will be offered to participate in this study by signing an informed consent. An informed consent approved by the Research Ethics Committee of the Virgen de la Arrixaca University Hospital will be used.

Patients who give their consent for the study will be randomized to the drainage group (D) and the control group without drainage (ND) before the beginning of the abdominal wall closure.

In the drainage group (D), it will be placed on the right flank / right iliac fossa. The drain will be connected to a bag and fixed to the skin with a silk. Said drain will be placed at the level of the surgical bed.

Regarding the control group, intraoperative drainage will not be placed, except when the surgeon's discretion considers it necessary due to the high risk of bleeding, bile leakage or any other process / complication in which it may benefit from intra-abdominal drainage.

All patients, regardless of the randomization group, will receive a quality of life questionnaire (SF-36) prior to surgery that they must complete.

All patients will receive routine antibiotic prophylaxis 60 minutes before surgery, repeating the number of doses that are required according to blood loss and surgical time. Antibiotic prophylaxis will be adjusted according to the resistance protocols of each participating center.

○ **DATA COLLECT**

The following variables will be collected for each patient:

- **Recipient preoperative** variables: gender, age, pre-transplant stay, BMI, ASA, diabetes, HTN, dialysis, MELD, Child-Pugh, serology, albumin, bilirubin, INR, CRP, creatinine, ascites, SBP, prothrombin time, encephalopathy, time from SSI to HT (months), retransplantation, previous surgeries, cirrhosis etiology, indication for transplantation, sarcopenia.
- **Donor** characteristic variables: age, stay in ICU, vasoactive drugs, cultures, antibiotics, CIT, WIT, type of donation (DBD / DCD), previous immunosuppression.
- **Intraoperative** variables: placement or not of abdominal drainage, surgical time (min), transfusions, blood loss, surgical technique, arterial anastomosis type, biliary anastomosis type, donation with extended criteria, recipient with extended criteria, clamping times.
- **Postoperative** variables: ICU stay, hospital stay, abdominal complications (collection, bile leak, hematoma, hemorrhage, paralytic ileus, ascites, bleeding, wound drainage complications, vascular anastomosis complications, mechanical

obstruction, hollow viscus perforations, wound complications surgery), graft function, post-transplant antibiotic therapy, post-transplant immunosuppressive regimen, number of post-HT HC, mortality at 90 days, global complications at 90 days.

○ **FOLLOW-UP**

The drain output will be evaluated daily after the surgical procedure. The quantity will be measured in milliliters and the appearance of the drainage will be categorized as serous, hematic, biliary or purulent. Its removal will be assessed on the 3rd postoperative day unless the patient shows signs of bleeding, bile leakage, intra-abdominal infection or any other complication that contraindicates its removal. When any of these complications that have delayed removal of the intra-abdominal drain are resolved, the drain should be removed.

Patients will be followed up during the postoperative period on a daily basis and complications will be observed at 90 days from discharge.

Calls will be made from discharge, the first 30 days every 15 days, from the month of discharge the periodicity will be monthly until 90 days from the intervention. The last follow-up call will be made on day 90. Subsequently, the follow-up protocol of each center will be followed.

The SF-36 quality of life questionnaire will be performed preoperatively, at one month and at 4 months after surgery.

○ **Sampling methods and assignment of subjects to groups. Randomization.**

Subjects will be recruited at the pre-liver transplant consultation and/or at the time of inclusion on the transplant waiting list (Liver Transplant Committee - General Surgery Sessions Room - 3rd Floor Hospital Clínico Universitario Virgen de la Arrixaca, Murcia - Tuesday at 12h) among those patients who meet the criteria for participation in the study.

Once the individual has signed the informed consent document for the study and it has been verified that they meet all the inclusion criteria and none of the exclusion criteria, they will be considered eligible to be included in the study. In this first contact with the patient, you will fill out a first SF-36 health questionnaire.

Each patient will be assigned a numerical code consecutively as they are included in the trial. Randomization should be done in the operating room at the time prior to abdominal wall closure (optimal time for drain placement). This moment is chosen for randomization to avoid randomizing patients who ultimately require drainage due to intraoperative conditions by decision of the surgeon and not by randomization. Randomization will be performed using a spreadsheet with restricted access to participating centers through simple randomization. In order to carry out the randomization, the sheet will require filling in the initial data of the patient with which it will be verified that he meets the inclusion criteria in the study and none of the exclusion criteria. Subsequently, he will proceed to randomization and assign a number to the patient.

- **STUDY POPULATION**

- **Definition of the study population**

Patients will be recruited into the transplantation committee of the Hospital Clínico Virgen de la Arrixaca University. 365 individuals will be selected from both sexes, aged between 18 and 75 years, diagnosed with cirrhosis, liver disease, fulminant hepatitis or other indications specific to HT.

- **Inclusion criteria.**

- Patients of both sexes aged between 18 and 75 years included in the waiting list for HT by the committee of the Virgen de la Arrixaca University Hospital.
- Sign Informed Consent.

- **Exclusion criteria.**

- Having been rejected for liver transplantation by said committee.
- Age less than 18 years or greater than 75.
- Any contraindication by the main surgeon that makes the placement of an intra-abdominal drain necessary.
- Not having signed the Informed Consent.

- **Abandonment and replacement of patients.**

Subjects can withdraw at any time, with or without reason, and without prejudice to them. The subject participating in the study may revoke his consent at any time, without expression of cause and without thereby incurring responsibility or harm to the participating subject. Individuals who drop out of the study will not undergo further follow-up or be substituted. The investigator may withdraw a subject from the study if he considers that the subject can no longer comply with all the requirements of the study or if any of the procedures is considered possibly harmful to him. Data that has already been collected on withdrawn subjects will be retained and used for analysis, but no new data will be collected after withdrawal.

- **Withdrawal criteria**

Those patients who meet any of these criteria will be withdrawn from the study:

- Presence of adverse events that at the discretion of the investigator implies the withdrawal of the patient.
- Deviation from the protocol that affects the interpretation of the study results and its scientific validity.
- Optional decision.
- Resignation of the individual to continue in the study.
- Loss of follow-up.

- **TREATMENT OF SUBJECTS**

- **Description of the intervention**

In the intervention group, intra-abdominal drainage will be placed in the right flank / right iliac fossa. This drain will be placed on the surgical bed and the extracorporeal end will drain into a collection bag. Control of the amount drained and the appearance of the content will be carried out on a daily basis. If the clinical situation of the patient allows it, the drain should be removed on the 3rd postoperative day. If the clinical status or complications do not allow its withdrawal, consider withdrawing it as soon as said contraindications allow it.

The control group will not receive drainage. The evolution and the appearance of complications will be monitored in the ICU and ward on a daily basis.

The subjects will be closely monitored through the daily visit to the ICU and ward.

Regarding the assessment of quality of life (SF-36), the patient will complete a questionnaire at various points in the process:

- Inclusion on the waiting list.
- One month after surgery.
- 4 months after surgery.

- **Management of investigational medications / products.**

Investigational products will be supplied by the hospital. Said product will be administered intraoperatively and supplied to the surgical ward when its placement is confirmed depending on the group assigned after randomization.

- **Previous and concomitant treatments.**

Any pharmacological treatment carried out during the experimental period must be registered in the CRD. The principal investigator of the study will judge the suitability of the participant's continuity in the study.

The taking of drugs or other treatments that may modify the biological effects of the products under investigation will not be explicitly allowed.

- **Rescue medication.**

The use of rescue medication required by the patient is contemplated: analgesia, antipyretics, albumin in abundant ascitic losses, ...

- **Compliance evaluation.**

Following the randomization plan, all patients will be evaluated daily during their stay in the ward. All files must be available for review by the Promoter or the Promoter's representative.

- **STUDY VARIABLES.**

The following variables will be collected for each patient:

- **Recipient preoperative** variables: gender, age, pre-transplant stay, BMI, ASA, diabetes, HTN, dialysis, MELD, Child-Pugh, serology, albumin, bilirubin, INR, CRP, creatinine, ascites, SBP, prothrombin time, encephalopathy, time from SSI to HT (months), retransplantation, previous surgeries, cirrhosis etiology, indication for transplantation, sarcopenia.
- **Donor** characteristic variables: age, stay in ICU, vasoactive drugs, cultures, antibiotics, CIT, WIT, type of donation (DBD / DCD), previous immunosuppression.
- **Intraoperative** variables: placement or not of abdominal drainage, surgical time (min), transfusions, blood loss, surgical technique, arterial anastomosis type, biliary anastomosis type, donation with extended criteria, recipient with extended criteria, clamping times.
- **Postoperative** variables: ICU stay, hospital stay, abdominal complications (collection, bile leak, hematoma, hemorrhage, paralytic ileus, ascites, bleeding, wound drainage complications, vascular anastomosis complications, mechanical obstruction, hollow viscus perforations, wound complications surgery), graft function, post-transplant antibiotic therapy, post-transplant immunosuppressive regimen, number of post-HT HC, mortality at 90 days, global complications at 90 days.
- **SF-36:** Physical function, physical role, body pain, general health, vitality, social function, emotional role, mental health (on inclusion in the waiting list, one month after surgery, 4 months after surgery).

- **SUBJECT FOLLOW-UP**

As we have previously indicated, patients will be evaluated daily by the research staff during their hospital stay. Those who were discharged before day 30 post-transplant will continue to contact the researchers by phone and report any event related to the insertion point of the drain.

Calls will be made from discharge, the first 30 days every 15 days, from the month of discharge the periodicity will be monthly until 90 days from the intervention. The last follow-up call will be made on day 90.

- **SAFETY ASSESSMENT (only for medicines, food or other therapeutic procedures).**

All patients assigned to the control group (DN) will be reevaluated intraoperatively. If, for obvious clinical reasons, the placement of the drain is required, said patient will be excluded from the study (randomization will not be carried out, so it would not be included in the RCT) and the drain will be placed.

Patient safety was not impaired at any point in the study, with the intervention group (D) being the routine procedure in LT and the control group (ND) re-evaluated intraoperatively.

- **STATISTICS**

- **Data handling**

The data collection will be carried out through a Data Collection Notebook, capturing all the data in it legibly and in blue pen. Subsequently, said data will be dumped into a CRD through a spreadsheet. This sheet allows online access for the different study participants, to perform randomization and assign the patient code and to enter the data of each of the included patients. Patients will be included without personal data or identification documents, only an identification code that will be assigned to each one at the time of randomization. Once the trial is finished, all the data collected in the database will be evaluated for the writing of the final report.

All the documentation related to the study will remain stored in the Investigator's File, in the participating center, under the custody of the Principal Investigator until the end of the study. Once the study is finished, the documentation will be indexed and transferred to the general file of the center, complying with the recommendations established with respect to the Good Clinical Practice Standards.

